#### 8.1.2.5 Hypothesis

The hypotheses to be evaluated in the analysis of the PFS are:

$$H_0: S(t)_{\text{cabozantinib}} = S(t)_{\text{placebo}}$$

$$H_A: S(t)_{\text{cabozantinib}} \neq S(t)_{\text{placebo}}$$

where  $S(t)_{\text{Cabozantinib}}$  and  $S(t)_{\text{Placebo}}$  are the survivor functions for PFS for the cabozantinib and placebo arms, respectively.

#### 8.1.2.6 Primary Analysis

The primary analysis of PFS (designated PFS-EP-1) is event-based and will be conducted after at least 193 events (progression per RECIST 1.1 per BIRC or deaths) have been observed in the ITT population. The actual number of events may be higher due to the logistics of identifying events and predicting cutoff dates for analysis.

The hypothesis testing between the two treatment arms will be performed using the stratified log-rank test with a 2-sided  $\alpha=0.04$  or 0.05 level of significance (see Section 8.2 for details

regarding the  $\alpha$ -level). The stratification factors are as described in Section 2.5 and the values used for analysis will be those recorded in the IRT.

The median duration of PFS and the associated 96% or 95% confidence interval (CI) for each treatment arm will be estimated using the Kaplan-Meier method. The stratified hazard ratio (HR) and its 96% or 95% CI will be estimated using a Cox proportional-hazard model with treatment group as the independent variable and stratified by the same randomization stratification factors as were used for the log-rank test.

If the p-value for the stratified log-rank test is less than the critical value for rejecting the null hypothesis and the HR ( $\lambda$  cabozantinib/  $\lambda$  placebo) is  $< 1$ , the null hypothesis will be rejected and it will be inferred that PFS is superior in the cabozantinib arm compared to the placebo arm.

The critical p-values (and observed HR) for rejecting the null hypothesis are described in Section 2.4 . The actual critical values will depend upon the true number of events observed at each analysis.

The above analysis will also be provided for the OITT population.

#### **8.1.2.7 Sensitivity Analyses**

Event and censoring definitions for the primary analysis (PFS-EP-1) and 3 sensitivity analyses (PFS-EP-2, PFS-EP-3, PFS-EP-4) directed at the primary estimated for PFS are provided in Table 8.

The three sensitivity analyses evaluate the impact of different assumptions or conditions that potentially influence the estimate of the primary estimand:

- The PFS-EP-2 definition evaluates the influence of potentially inconsistent tumor assessment intervals between arms. For subjects who experience radiographic progression, it assigns the date of the scheduled visit as the event date, rather than the date of recorded progression.
- The PFS-EP-3 definition evaluates the influence of the assessor of radiographic progression, and is based up RECIST 1.1 evaluations by the investigator rather than the BIRC.
- The PFS-EP-4 definition evaluates the influence of the missing tumor assessments. It classifies subjects who experience  $\geq 2$  consecutive missing scheduled ATA

immediately prior to documented radiographic progression as having an event, rather than being censored, at the date of the last ATA prior to the missing visits.

Event and censoring definitions for 3 supplemental analyses (PFS-EA1-1, PFS-EA2-1, PFS-EA2-1) directed at the two alternative estimands for PFS are provided in Table 9.

- The PFS-EA1-1 definition is the primary analysis of alternative estimand 1.
- The PFS-EA2-1 definition is the primary analysis of alternative estimand 2.
- The PFS-EA2-2 definition is a sensitivity analysis of alternative estimand 2, similar to PFS-EP-4 (defined above).

Four additional “differential” sensitivity analyses (PFS-EP-11, PFS-EP-12, PFS-EP-13, PFS-EP-14) directed at the primary estimand will be conducted to evaluate the impact of potentially informative censoring. These analyses are based on the primary analysis PFS-EP-1 but with selected censored subjects re-classified as events, differentially by treatment arm, as shown in Table 10. These are highly conservative definitions intended to evaluate potential bias. The directions of treatment effects are of key interest rather than the values of inferential statistics.

All sensitivity and supplemental analyses will include all subjects in the ITT population. Tabulated summaries of survival times, hazard ratios, and log rank test statistics as well as graphs of survival functions will be presented.

The concordance in assessment of radiographic progression and the date between BIRC and investigator will be summarized for the ITT population.

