#### 8.1.2.4 Primary Definition

For the primary analysis directed toward the primary estimand, duration of PFS is defined as the time from randomization to the earlier of either the date of radiographic progression per BIRC or the date of death due to any cause.

$$\text{PFS (months)} = (\text{earliest date of progression, death, censoring} - \text{date of randomization} + 1) / 30.4375$$

General censoring rules for the primary analysis of PFS are described below, with details provided in Table 8(analysis ID PFS-EP-1):

- Subjects who receive systemic NPACT, or local NPACT for disease under study, or non-protocol radiation therapy for disease under study (other than to bone) or surgery to resect target lesions before experiencing an event will be right censored at the date of the last ATA on or prior to the date of initiation of subsequent therapy/surgery. If there is no such tumor assessment after randomization, the subject will be right censored on the date of randomization.
- Subjects who have not experienced an event (and are not otherwise censored) at the time of data cutoff will be right censored on the date of their last tumor assessment after randomization that is on or prior to the data cutoff. If there is no such tumor assessment after randomization, the subject will be right censored on the date of randomization.
- Subjects who miss two or more ATAs (operationally defined as an interval of 126 days in the first year and 196 days after the first year without an ATA) followed by an event (progression or death) will be right censored on the date of their most-recent ATA prior to the missing assessments. If there is no such tumor assessment after randomization, the subject will be right censored on the date of randomization.

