| ≥ 2 consecutive missing scheduled ATA immediately prior to analysis event              | censored        | date of last ATA* before missing visits                                  | censored                      | date of last ATA* before missing visits                                  | censored               | date of last ATA* before missing visits                                  | event                                      | date of last ATA* before missing visits                                  |
| Observation ongoing  |                 |  |                               |  |                        |  |  |  |
| None of the above  | censored        | date of last ATA*  | censored                      | date of last ATA*  | censored               | date of last ATA*  | censored                                   | date of last ATA*  |

ATA, adequate tumor assessment; BIRC, blinded independent review committee; ITT, intent-to-treat; NA, not applicable; PD, progressive disease; NPACT, non-protocol anti-cancer therapy (medications including radiopharmaceuticals but excluding local radiation)

Date of recorded PD = see SAP text.

\* or date of randomization if no post-randomization ATA

Blue cells indicate changes from primary analysis.

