| Local NPACT for disease under study (medications)                                      | event                            | date of first initiation of therapy                  | censored  | date of last ATA* before first initiation of therapy | censored  | date of last ATA* before first initiation of therapy |
| Surgical resection of target tumor lesion(s)   | event                            | date of last ATA* before target lesion resection     | censored  | date of last ATA* before target lesion resection     | censored  | date of last ATA* before target lesion resection     |
| Local radiation: to soft tissue for disease under study                                | event                            | date of last ATA* before non-target lesion resection | censored  | date of last ATA* before non-target lesion resection | censored  | date of last ATA* before non-target lesion resection |
| Missing data   |                                  |  |   |  |   |  |
| No baseline ATA  | censored                         | date of rand.  | censored  | date of rand.  | censored  | date of rand.  |
| ≥ 2 consecutive missing scheduled ATA immediately prior to analysis event              | censored                         | date of last ATA* before missing visits              | censored  | date of last ATA* before missing visits              | event   | date of last ATA* before missing visits              |
| Observation ongoing  |                                  |  |   |  |   |  |
| None of the above  | censored                         | date of last ATA*                                    | censored  | date of last ATA*                                    | censored  | date of last ATA*                                    |

ATA, adequate tumor assessment; BIRC, blinded independent review committee; ITT, intent-to-treat; NA, not applicable; PD, progressive disease; NPACT, non-protocol anti-cancer therapy (medications including radiopharmaceuticals but excluding local radiation)

Date of recorded PD = see SAP text.

\* or date of randomization if no post-randomization ATA

Blue cells indicate changes from primary analysis.

**Table 10: Definitions for Differential Sensitivity Analyses of PFS to Further Evaluate Potentially Informative Censoring (based on PFS-EP-1)**

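### After two missed scans, Tables 8 and 9 date known deaths and new-therapy starts at least 126 days too early in PFS-EP-4 and PFS-EA2-2, and conflict with the SAP's own text and Death row

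*Combined protocol and SAP*

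**What the plan says.** The primary PFS rule (SAP 8.1.2.4) treats two missed ATAs as a gap, "operationally defined as an interval of 126 days in the first year and 196 days after the first year without an ATA". If progression or death follows such a gap, the subject is censored at the last ATA before it.

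Table 8 carries this as the row "≥ 2 consecutive missing scheduled ATA immediately prior to analysis event". In the PFS-EP-1 column the outcome is censoring. In the PFS-EP-4 column it is an event, dated "date of last ATA* before missing visits". The asterisk adds "or date of randomization if no post-randomization ATA". Table 9 repeats the row, footnote and dating for PFS-EA2-2, which the text introduces thus: "The PFS-EA2-2 definition is a sensitivity analysis of alternative estimand 2, similar to PFS-EP-4 (defined above".

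Two other places point elsewhere. The PFS-EP-4 text in 8.1.2.7 classifies the subject "as having an event, rather than being censored, at the date of the last ATA prior to the missing visits", but limits the rule to gaps "immediately prior to documented radiographic progression as having an event, rather than being censored", so it does not mention deaths. The Death row of Table 8 uses the date of death in every column, PFS-EP-4 included. Table 9 likewise has separate rows dating death and the start of systemic non-protocol anticancer therapy (NPACT) when they occur. Neither table says which row prevails when two apply.

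In the PFS-EA1-1 column of Table 9, systemic and local NPACT are events dated at initiation. Target-lesion resection is an event dated "date of last ATA* before target lesion resection". Soft-tissue radiation is an event dated at the last ATA before a resection of non-target lesions, which is a different procedure.

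**The concern.** Table 8 gives the purpose of PFS-EP-4 as checking for informative censoring. A useful check counts the late event that the primary analysis discards. Here the event is counted at a visit where the subject was documented free of progression, or at randomization. For a death or a therapy start there is no uncertainty to justify that: the date is on the case report form.

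Survival times, hazard ratios and curves will be reported for each of these analyses, so misplaced event times would be visible in the study report. Missed scans are also a live issue, because SAP 9.9 foresees looking at missing-data patterns caused by the pandemic. Finally, because text, Death row and missing-ATA row disagree, two programmers could date the same death differently and each could cite the SAP.

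**Working it through.** **1. The gap.** Two scan intervals plus their windows: 2 × (56 + 7) = 126 days on the 8-weekly schedule, and 2 × (84 + 14) = 196 days on the 12-weekly schedule. Both match SAP 8.1.2.4, so any event moved to the last ATA moves back by at least these amounts (126/30.4375 = 4.1 months; 196/30.4375 = 6.4 months).

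**2. Which row governs a death.** The PFS-EP-1 column has the same Death row, yet 8.1.2.4 censors a death that follows a gap. In that column the missing-ATA row therefore overrides the Death row. PFS-EP-4 has the same layout, so the most coherent reading of the table also moves a late death to the last ATA. The PFS-EP-4 text does not confirm this.

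**3. One subject.** PFS in months = (assigned date − randomization date + 1)/30.4375. A death at month 10 falls at 10 × 30.4375 ≈ 304 days. With no post-randomization ATA, the table assigns the randomization date: (0 + 1)/30.4375 = 0.03 months, about 303 days early.

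**4. Which dates are known.** Death and NPACT start: known. Progression first seen after a gap: onset lies between the last clean scan (early bound) and the scan that showed it (late bound). Neither is the true date.

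**5. Effect on the results.** Simulation of 600 trials per scenario, using the SAP's 200:100 subjects, medians of 9.0 and 5.5 months (5.5 in both arms for the null), 15-month accrual, cutoff at month 20 and scan schedule, with an unstratified Cox model. Assumptions not in the documents: the gap rates; 15% of events are deaths; the last ATA is drawn at random among scans at least 126 days before the event; 126 days is used throughout. All events after a gap, progression and death, are moved as the tables say.

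| Planned effect | Gap rate, cabozantinib / placebo | HR, recorded date | HR, last ATA | Change |
|---|---|---|---|---|
| HR 0.61 | 5% / 5% | 0.632 | 0.634 | +0.002 |
| HR 0.61 | 10% / 10% | 0.627 | 0.631 | +0.004 |
| HR 0.61 | 20% / 20% | 0.628 | 0.634 | +0.006 |
| HR 0.61 | 15% / 5% | 0.630 | 0.658 | +0.028 |
| HR 0.61 | 5% / 15% | 0.630 | 0.611 | −0.019 |
| Null | 20% / 20% | 1.002 | 0.999 | −0.003 |
| Null | 15% / 5% | 0.998 | 1.037 | +0.039 |
| Null | 5% / 15% | 0.999 | 0.961 | −0.038 |

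Medians fall even when gaps are equal. At 5%, 10% and 20% in both arms (HR 0.61), the cabozantinib median goes from 9.50 to 9.38, 9.60 to 9.36 and 9.54 to 9.05 months. The placebo median goes from 6.21 to 6.04, 6.24 to 5.90 and 6.24 to 5.44.

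**6. Limit of that simulation.** It takes the recorded date as the benchmark, as if the gap had not delayed detection. A second simulation lets two missed scans span the progression, which is found at the next scan (again 15% deaths). Under the null with gaps of 15% on placebo and 5% on cabozantinib, recorded dates give 1.03 and last-ATA dates 0.99; with the rates reversed, 0.97 and 1.01. With a true HR of 0.80 and 15% / 5%, the HR is 0.816 with no gaps, 0.840 with recorded dates and 0.811 with last-ATA dates. For progression, then, the recorded date can distort more than the last ATA.

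**The case against.** The strongest defence is that PFS-EP-4 keeps the primary analysis's date and changes only the status from censored to event, which isolates the censoring decision. For progression that is reasonable: the last ATA is a legitimate early bound, and step 6 shows it can be the less distorting choice. A reader might infer that the recorded progression date is the true one and that using it removes all error. The gap itself rules that out. The defence does not reach deaths or NPACT starts, whose dates are known.

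It can also be said that the PFS-EP-4 text names progression only and the Death row uses the date of death, so late deaths may never have been meant to move. That is possible, but the missing-ATA row says otherwise, and the primary column shows that row prevailing. The contradiction needs settling under either intention.

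A reader might further infer that the rule is biased towards cabozantinib because the protocol expects more dropout on placebo. The documents do not support this. Protocol Sections 1.5.5 and 5.3 offer crossover to minimize the potential for differential dropout; they do not predict it. Dropout is also not the same as a gap followed by an observed event. If cabozantinib subjects miss more scans, the rule works against cabozantinib. Nor does the SAP call PFS-EP-4 conservative; it reserves that description for PFS-EP-11 to PFS-EP-14.

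Finally, these analyses carry no alpha (SAP 8.2 treats everything beyond the two primary tests as exploratory), and PFS-EP-11 to PFS-EP-14 also probe informative censoring. Both points stand and limit the weight of this one. But none of the Table 10 categories is defined by missed scans followed by an event, so those analyses do not replace PFS-EP-4.

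**Conclusion.** The point holds for the dating rule and the contradiction, not as a general charge of bias. Under Tables 8 and 9, a death after a gap in either analysis, or a systemic NPACT start after a gap in PFS-EA2-2, is placed at least 126 days too early (196 after year 1), and at Day 1 if there was no post-randomization ATA. The text and the Death row disagree with this, and no precedence is given.

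Relative to recorded dates, event times and medians move early: about 0.1 to 0.8 months at assumed gap rates of 5% to 20%. The hazard ratio changes by 0.006 or less when gaps are equally common. It changes by about 0.02 to 0.04, against the arm with more gaps, for an assumed 10-point difference. These figures cover all back-dated events, so deaths and therapy starts alone would account for only part of them, and they take the recorded date as correct. The documents give no gap rates and do not say which arm would have more.

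The primary PFS test is unaffected. The correction is worth making because it costs little and the rule as tabulated produces event times known to be wrong.

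**What to change.** - **Precedence.** State in Tables 8 and 9 which row prevails when an event follows two or more missed ATAs, and align the PFS-EP-4 text in 8.1.2.7 with the tables, naming deaths explicitly.
- **Deaths and NPACT starts.** In PFS-EP-4 date a death after a gap at the date of death. In PFS-EA2-2 do the same, and date a systemic NPACT start at initiation.
- **Progression after a gap.** Report it at the recorded date, which fits the analysis's own name, and run last-ATA dating as a separately labelled early bound. The two versions bracket onset and neither is presented as the true date.
- **PFS-EA1-1.** Date target-lesion resection and soft-tissue radiation when they occurred, as the NPACT rows in that column already do, and remove the stray reference to non-target resection from the radiation cell.

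Cost: a few table cells, one sentence and one extra run. The dates of progression, death and therapy start are already used elsewhere in the SAP's rules.

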**Table 8: Event and Censoring Rules for Primary and Sensitivity Analyses of Primary PFS Estimand**

| Estimand   | Primary         |  | Primary                       |  | Primary                |  | Primary                                    |  |
|--|-----------------|--|-------------------------------|--|------------------------|--|--|--|
| Analysis type  | Primary         |  | Sensitivity                   |  | Sensitivity            |  | Sensitivity                                |  |
| Analysis purpose   | Primary         |  | Evaluate assessment time bias |  | Evaluate assessor bias |  | Evaluate potentially informative censoring |  |
| Analysis ID  | PFS-EP-1        |  | PFS-EP-2                      |  | PFS-EP-3               |  | PFS-EP-4                                   |  |
| Analysis name  | rPFS per BIRC   |  | Uniform dates                 |  | rPFS per Investigator  |  | rPFS per BIRC despite missing ATA          |  |
| Estimand endpoint  | Radiographic PD |  | Radiographic PD               |  | Radiographic PD        |  | Radiographic PD                            |  |
| Population   | ITT             |  | ITT                           |  | ITT                    |  | ITT  |  |
| Situation  | Outcome         | Date of Outcome  | Outcome                       | Date of Outcome  | Outcome                | Date of Outcome  | Outcome                                    | Date of Outcome  |
| Radiographic PD per RECIST 1.1 per BIRC  | Event           | date of recorded PD  | event                         | date of scheduled visit (or next scheduled visit if between visits)      | NA                     | NA   | event                                      | date of recorded PD  |
| Radiographic PD per RECIST 1.1 per Investigator  | NA              | NA   | NA                            | NA   | event                  | date of recorded PD  | NA   | NA   |
| Death  | event           | date of death  | event                         | date of death  | event                  | date of death  | event                                      | date of death  |
| Intercurrent events (excluding those with Treatment Policy strategy for all estimands) |                 |  |                               |  |                        |  |  |  |
| Clinical deterioration   | NA              | NA   | NA                            | NA   | NA                     | NA   | NA   | NA   |
| Systemic NPACT (medications)   | censored        | date of last ATA* before first initiation of therapy                     | censored                      | date of last ATA* before first initiation of therapy                     | censored               | date of last ATA* before first initiation of therapy                     | censored                                   | date of last ATA* before first initiation of therapy                     |
| Local NPACT for disease under study (medications)                                      | censored        | date of last ATA* before first initiation of therapy                     | censored                      | date of last ATA* before first initiation of therapy                     | censored               | date of last ATA* before first initiation of therapy                     | censored                                   | date of last ATA* before first initiation of therapy                     |
| Surgical resection of target tumor lesion(s)   | censored        | date of last ATA* before target lesion resection                         | censored                      | date of last ATA* before target lesion resection                         | censored               | date of last ATA* before target lesion resection                         | censored                                   | date of last ATA* before target lesion resection                         |
| Local radiation: to soft tissue for disease under study                                | censored        | date of last ATA* local radiation of soft tissue for disease under study | censored                      | date of last ATA* local radiation of soft tissue for disease under study | censored               | date of last ATA* local radiation of soft tissue for disease under study | censored                                   | date of last ATA* local radiation of soft tissue for disease under study |
| Missing data   |                 |  |                               |  |                        |  |  |  |
| No baseline ATA  | censored        | date of rand.  | censored                      | date of rand.  | censored               | date of rand.  | censored                                   | date of rand.  |
| ≥ 2 consecutive missing scheduled ATA immediately prior to analysis event              | censored        | date of last ATA* before missing visits                                  | censored                      | date of last ATA* before missing visits                                  | censored               | date of last ATA* before missing visits                                  | event                                      | date of last ATA* before missing visits                                  |
| Observation ongoing  |                 |  |                               |  |                        |  |  |  |
| None of the above  | censored        | date of last ATA*  | censored                      | date of last ATA*  | censored               | date of last ATA*  | censored                                   | date of last ATA*  |

ATA, adequate tumor assessment; BIRC, blinded independent review committee; ITT, intent-to-treat; NA, not applicable; PD, progressive disease; NPACT, non-protocol anti-cancer therapy (medications including radiopharmaceuticals but excluding local radiation)

Date of recorded PD = see SAP text.

\* or date of randomization if no post-randomization ATA

Blue cells indicate changes from primary analysis.

